7.2.3 Reporting of Pregnancy and Lactation to the Sponsor

Although pregnancy and lactation are not considered adverse events, it is the responsibility of investigators or their designees to report any pregnancy or lactation in a subject (spontaneously reported to them), including the pregnancy of a male subject's female partner that occurs during the trial.

Pregnancies and lactations of subjects and female partners of male subjects from the time the documented informed consent form is provided but before treatment allocation/randomization must be reported by the investigator if they cause the subject to be excluded from the trial or are the result of a protocol-specified intervention, including but not limited to washout or discontinuation of usual therapy, diet, placebo treatment or a procedure.

Pregnancies and lactations of subjects and female partners of male subjects that occur from the time of treatment allocation/randomization through 180 days following cessation of Sponsor's product must be reported. All reported pregnancies must be followed to the completion/termination of the pregnancy. Pregnancy outcomes of spontaneous abortion, missed abortion, benign hydatidiform mole, blighted ovum, fetal death, intrauterine death, miscarriage and stillbirth must be reported as serious events (Important Medical Events). If the pregnancy continues to term, the outcome (health of infant) must also be reported.

Such events must be reported within 24 hours to the Sponsor either by electronic media or paper. Electronic reporting procedures can be found in the EDC data entry guidelines. Paper reporting procedures can be found in the Investigator Trial File Binder (or equivalent).

7.2.4 Immediate Reporting of Adverse Events to the Sponsor

7.2.4.1 Serious Adverse Events

A serious adverse event is any adverse event occurring at any dose or during any use of Sponsor's product that:

- Results in death;
- Is life threatening;
- Results in persistent or significant disability/incapacity;
- Results in or prolongs an existing inpatient hospitalization;
- Is a congenital anomaly/birth defect;
- Is an other important medical event.

Note: In addition to the above criteria, adverse events meeting either of the below criteria, although not serious per ICH definition, are reportable to the Sponsor in the same timeframe as SAEs to meet certain local requirements. Therefore, these events are considered serious by the Sponsor for collection purposes.

- Is a new cancer (that is not a condition of the study);
- Is associated with an overdose.

Refer to [Table 23](#) for additional details regarding each of the above criteria.

For the time period beginning when the consent form is signed until treatment allocation/randomization, any serious adverse event, or follow up to a serious adverse event, including death due to any cause other than progression of the cancer under study (reference Section 7.2.4.3 for additional details), that occurs to any subject must be reported within 24 hours to the Sponsor if it causes the subject to be excluded from the trial, or is the result of a protocol-specified intervention, including but not limited to washout or discontinuation of usual therapy, diet, placebo treatment or a procedure.

For the time period beginning at treatment allocation/randomization through 90 days following cessation of trial treatment, or 30 days following cessation of trial treatment if the subject initiates new anticancer therapy, whichever is earlier, any serious adverse event, or follow up to a serious adverse event, including death due to any cause other than progression of the cancer under study (reference Section 7.2.4.3 for additional details), whether or not related to the Sponsor's product, must be reported within 24 hours to the Sponsor either by electronic media or paper. Electronic reporting procedures can be found in the EDC data entry guidelines. Paper reporting procedures can be found in the Investigator Trial File Binder (or equivalent).

All serious adverse events that are considered to be post-surgical complications by the investigator, from the time of protocol-specified surgery through 90 days following surgery or 30 days following protocol-specified surgery if the subject initiates new anticancer therapy, whichever is earlier, must be reported by the investigator.

Additionally, any serious adverse event, considered by an investigator who is a qualified physician to be related to the Sponsor's product that is brought to the attention of the investigator at any time following consent through the end of the specified safety follow-up period specified in the paragraph above, or at any time outside of the time period specified in the previous paragraph also must be reported immediately to the Sponsor. Subjects in post-treatment follow-up will be actively followed for treatment-related late serious adverse events for up to 5 years.

All subjects with serious adverse events must be followed up for outcome.

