3.3 Exploratory Objectives

(1) **Objective:** In subjects treated with pembrolizumab in combination with CRT and subjects treated with placebo in combination with CRT, to compare:

- Local Regional Control
- Distant Metastases Free Survival
- Incidence of second Head and Neck and Other Cancers

(2) **Objective:** In subjects treated with pembrolizumab in combination with CRT and subjects treated with placebo in combination with CRT, to evaluate the relationship:

- between genetic variation and clinical outcome
- between DNA mutational burden and RNA analysis and clinical outcome

(3) **Objective:** To characterize utilities using the EuroQoL EQ-5D.

(4) **Objective:** To identify molecular (genomic, metabolic and/or proteomic) biomarkers that may be indicative of clinical response/resistance, safety, pharmacodynamic activity, and/or the mechanism of action of pembrolizumab in combination with CRT and other treatments.

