7.1.8.3.2 Safety Follow-up Visit

The mandatory 30-Day Safety Follow-Up Visit should be conducted 30 days after the last dose of trial treatment or before the initiation of a new anticancer treatment, whichever comes first. All AEs that occur prior to the 30-Day Safety Follow-Up Visit should be recorded.

Additionally, subjects in Post-Treatment Follow-Up will be followed for treatment-related late toxicities meeting serious criteria for up to 5 years and should be recorded.

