7.1.8.3.4 Survival Follow-up Assessments

Once a subject experiences an event/disease progression as defined in the EFS Section 8.4.1.1, the subject enters the Survival Follow-Up Phase and should be contacted by telephone or have their medical records reviewed every 3 months (± 7 days) during Follow-Up Years 1 through 3 and every 6 months (± 14 days) during Follow-Up Years 4 through 5 and every 6 months (± 28 days) after Follow-Up Year 5 to assess for survival status until death, withdrawal of consent or the end of the study, whichever occurs first. Assessment of overall survival should also include evaluation for whether other anticancer therapy has been initiated. When assessing for survival status for subjects in survival follow-up who have not yet experienced an event/PD, also evaluate for whether the subject has had additional imaging assessments or experienced biopsy and/or surgery confirmed progression. The Sponsor may request survival status to be assessed at additional time points during the course of the study. For example, survival status may be requested prior to the eDMC safety review, efficacy interim analyses and final analysis. All subjects who are in the Survival Follow-Up Phase and not known to have died prior to the request for these additional survival status time points will be contacted or have their medical records reviewed at that time. These additional assessments will have no effect on the schedule for the protocol-specified Survival Follow-Up Phase, i.e., the schedule for Survival Status (see Section 6.3 - Post-Treatment Efficacy Follow-up Visits) will continue as planned whether or not an additional survival status assessment is conducted.

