7.1.9.8 Distant Metastasis Free Survival

Distant metastasis free survival is defined as the time from the date of randomization to the date of first record of appearance of distant metastasis or death for any cause. Locoregional failure or second cancers diagnosed before the distant metastases are not considered events of interest for this endpoint.

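### Second cancers are an exploratory between-arm comparison, but any-cause reporting of new cancers ends 90 (or 30) days after treatment, so longer-term incidence would be incomplete

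*Combined protocol and SAP*

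**What the plan says.** Section 3.3 of the protocol includes, under a heading of comparisons between the two arms, "Incidence of second Head and Neck and Other Cancers". The objective is exploratory and carries no hypothesis, alpha or sample size.

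The rule that names a new cancer for collection is in Section 7.2.4.1 and is repeated in Table 23. New cancers other than the study cancer "are reportable to the Sponsor in the same timeframe as SAEs to meet certain local requirements". Regardless of relatedness, that timeframe is the one "beginning at treatment allocation/randomization through 90 days following cessation of trial treatment". A subject who goes on to another anticancer therapy has a shorter limit, 30 days after stopping.

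Once the window closes, the obligation narrows to events judged related:

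- Section 7.2.4.1 makes related serious events reportable whenever they come to the investigator's attention, with active follow-up for up to 5 years.
- Section 7.1.8.3.2 says subjects in post-treatment follow-up will be "followed for treatment-related late toxicities meeting serious criteria for up to 5 years".
- Section 7.1.2.1 ends with the same restriction to related serious late toxicity.
- Footnote d of flow chart 6.3 has it too, but as something that may be collected.

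Survival contacts (Sections 7.1.1.8 and 7.1.8.3.4, flow chart 6.3 footnote b) ask about vital status and, in subjects still event-free, evidence of an EFS event. They also ask about later treatment: "Assessment of overall survival should also include evaluation for whether other anticancer therapy has been initiated". None asks about a new primary.

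Sections 7.1.9.6 to 7.1.9.9 define EFS, locoregional control, distant metastasis free survival and OS. No section defines the second-cancer endpoint. Section 8.6.1 defers methods for exploratory objectives to the supplemental SAP, which is not among the documents.

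**The concern.** The protocol states a comparison that its own collection rules support only while subjects are on treatment and shortly afterwards. Take a new primary that appears two or three years after randomization and that the investigator considers unrelated. No stated rule requires it to be recorded as a second cancer.

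Two features make the shortfall more than a shorter observation period. The window closes relative to each subject's own stopping date, so its length depends on progression, toxicity and new therapy. After it closes, whether a cancer is counted depends on a relatedness judgement. Incidence from the resulting data would be truncated at different times in different subjects and then continued for a selected subset. An analysis plan cannot recover diagnoses that were never collected.

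**Working it through.** The documents give no expected rate, event count or power for second cancers, so there is no figure of the plan's to reproduce. The check has two parts: the length of the any-cause window, and its share of time alive.

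**1. Length of the window.** Doses are every 21 days, up to 17 (Table 2). Taking the last pembrolizumab/placebo dose as the end of trial treatment and 30.4375 days per month, the window closes at (doses − 1) × 21 + 90 days from first dose, or + 30 days if new therapy starts.

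| Doses | Last dose (day) | + 90 days | + 30 days |
|---|---|---|---|
| 17 | 336 | 426 days = 14.0 months | 366 days = 12.0 months |
| 9 | 168 | 258 days = 8.5 months | 198 days = 6.5 months |
| 3 | 42 | 132 days = 4.3 months | 72 days = 2.4 months |

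Interruptions lengthen the 17-dose figure. In the 3-dose case, finishing standard-fractionation radiotherapy in study Week 8 could move the end of treatment up to about two weeks later. The final analysis is planned at about 60 months, with at least 35 months of follow-up for every subject (Section 8.1).

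**2. Share of time alive.** Inputs from Section 8.9:

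- control EFS 70% at 12 months; EFS hazard ratio 0.70
- control OS 85%, 65% and 48% at 12, 36 and 96 months; OS hazard ratio 0.71

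Assumption: treatment stops at the EFS event or at dose 17, taken as 11.1 months, and reporting runs 3 months more.

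- Control EFS hazard in year 1: λ = −ln(0.70)/12 = 0.02972 per month. For pembrolizumab: 0.70 × 0.02972 = 0.02081.
- Mean time on treatment = (1 − exp(−11.1λ))/λ = 9.45 months (control) and 9.91 (pembrolizumab).
- Mean window = 9.45 + 3 = 12.45 and 9.91 + 3 = 12.91 months. The difference between arms is 0.46 month.
- Control OS hazards: −ln(0.85)/12 = 0.01354; −ln(0.65/0.85)/24 = 0.01118; −ln(0.48/0.65)/60 = 0.00505. Pembrolizumab hazards are these times 0.71.
- Mean time alive is the area under the OS curve. Control to 36 months: 0.15/0.01354 + 0.20/0.01118 = 11.08 + 17.89 = 28.97. From 36 to 60 months, with S(60) = 0.65 × exp(−24 × 0.00505) = 0.576, the area adds 14.69, giving 43.66. Pembrolizumab: 30.80 and 47.74.

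| Horizon | Control | Pembrolizumab |
|---|---|---|
| 36 months | 12.45/28.97 = 43.0% | 12.91/30.80 = 41.9% |
| 60 months | 12.45/43.66 = 28.5% | 12.91/47.74 = 27.0% |

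Using exactly 336 and 90 days lowers each ratio by at most 0.3 percentage points. If the 30-day rule applied to everyone (9.45 + 0.99 = 10.44 and 9.91 + 0.99 = 10.90 months), the shares would be 35-36% at 36 months and 23-24% at 60.

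**3. Cross-check with staggered entry.** Planned accrual, rescaled to 780, was combined with the same OS assumptions, with and without the 3% yearly dropout. If every subject completed 17 doses (14.0-month window), the window would cover 35-38% of person-time alive to calendar month 60 and 24-28% to month 84. If every subject stopped after 3 doses, it would cover about 6-13% to month 60, the lower end being the 30-day rule.

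**The case against.** **Other text is broader.** Section 7.1.2.1 says adverse events are recorded during the follow-up period, and flow chart 6.3 lists adverse event review as continuous. But the same paragraphs of 7.1.2.1 end by limiting late recording to related serious toxicity, Section 7.2 ends all-event reporting at 30 days, and the flow-chart row carries footnote d. At most this is a conflict to be reconciled, and it does not supply a collection rule.

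**Indirect routes exist.** Later anticancer therapy is recorded (Section 7.1.1.7), imaging continues in event-free subjects (Section 7.1.8.3.3.1), and tissue goes to the central laboratory if a biopsy shows invasive cancer (flow chart 6.3, footnote h). This stands in part: many new primaries would leave some trace, and the case report forms are not among the documents. A reader might infer that nothing is recorded after the window, and that is not shown. Still, Section 7.1.1.7 captures medication rather than diagnosis, scheduled imaging ends at an EFS event and covers only head and neck, chest and upper abdomen, and no text tells sites to record what is found as a second primary.

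**The objective is exploratory.** This stands. It lowers the weight of the point, but the collection gap remains.

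**The size is model-based.** This also stands. The model in step 2 adds 3 months after every EFS event, including deaths, and ignores stopping for toxicity. Both overstate coverage. Its 60-month horizon ignores staggered entry, which step 3 allows for. A reader might convert the 60-month figure into about 70% of second cancers missed. That needs a constant rate and no capture at all outside the window, and the documents support neither.

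**Distant metastasis free survival.** A reader might infer that this endpoint suffers from missing second-cancer dates. Section 7.1.9.8 says: "Locoregional failure or second cancers diagnosed before the distant metastases are not considered events of interest for this endpoint". They neither end nor censor it, so it needs no such dates.

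**Conclusion.** The point holds as a gap in long-term collection. The protocol requires any-cause recording of new cancers for roughly 14 months at most after uninterrupted completion of 17 doses, and for less after early stopping. On the plan's own survival assumptions this is about 42-43% of time alive over 36 months and 27-29% over 60 months. The figures rest on the stopping assumption in the working and are illustrative. The documents give neither a second-cancer rate nor a discontinuation rate.

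Beyond the window, incidence would be incomplete and would depend on when treatment stopped and on a causality judgement.

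Two stronger readings are not supported. The objective is not unanswerable: incidence on treatment and shortly after is captured whatever the cause, and related cancers remain reportable later. Nor does the model show a material difference between arms in window length, since 0.46 month is small; the concern about unequal ascertainment rests on the dependence on stopping date and relatedness. EFS, OS and distant metastasis free survival are unaffected.

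**What to change.** - In Sections 7.1.8.3.3 and 7.1.8.3.4 and flow chart 6.3, record any new primary malignancy (date, site, histology) regardless of relatedness. Do this at every existing follow-up visit and survival contact, including after an EFS event, until death, withdrawal or end of study.
- In Section 7.1.9, define the endpoint as time from randomization to first second primary, with death as a competing event, and report cumulative incidence by arm.
- Reconcile Section 7.1.2.1 with footnote d of flow chart 6.3, Section 7.2 and Section 7.2.4.1, including whether late related serious events must or may be collected.
- If this is not collected, restrict the objective in Section 3.3 to the any-cause reporting window and say so when reporting it.

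Amendment 08 follows the final efficacy analysis, but survival contacts continue past year 5 (flow chart 6.3, footnote b). Subjects still in contact can therefore be asked about earlier new primaries. For those who have died or left, recovery would be partial at best.

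The cost is one form and one question at contacts already scheduled every 3 or 6 months, plus protocol wording. The downside is slightly more site data entry and medical coding.

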3.2 Secondary Objective(s) & Hypothesis(es)

(1) **Objective:** To compare overall survival (OS) in subjects treated with pembrolizumab in combination with CRT and subjects treated with placebo in combination with CRT.

Hypothesis: Pembrolizumab in combination with CRT is superior to placebo in combination with CRT with respect to OS.

(2) **Objective:** To evaluate and compare the safety and tolerability profile of pembrolizumab in combination with CRT and subjects treated with placebo in combination with CRT.

(3) **Objective:** To compare mean change from baseline in Global health status/quality of life (QoL) and physical functioning using the EORTC QLQ-C30, and swallowing, speech and pain symptoms using the EORTC QLQ-H&N35 in subjects treated with pembrolizumab in combination with CRT and subjects treated with placebo in combination with CRT.

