- Noncompliance with trial treatment or procedure requirements
- Completed 17 doses of treatment with pembrolizumab/placebo

Note: 17 doses of study medication (pembrolizumab/placebo) are calculated in 3-week intervals from the date of first dose.

- Administrative reasons

The End of Treatment and Follow-up Visit procedures are listed in Section 6 (Trial Flow Chart) and Section 7.1.8 (Visit Requirements). After the end of treatment, each subject will be followed for 30 days for AE monitoring (serious adverse events will be collected for 90 days after the end of treatment as described in Section 7.2.4.1). Subjects who discontinue for reasons other than PD/event will have post-treatment follow-up for disease status until experiencing an event/disease progression, withdrawing consent or becoming lost to follow-up. After documented disease progression each subject will be followed by telephone for survival until death, withdrawal of consent, or the end of the study, whichever occurs first.

Subjects who discontinue trial treatment for a reason other than either experiencing an event/disease progression or starting a new anticancer therapy will move into the Post-Treatment Efficacy Follow-Up Phase to be assessed every 3 months (91 ± 7 days) for Follow-up Years 1 through 3 and then every 6 months (± 14 days) for Follow-up Years 4 through 5 and every 6 months (± 28 days) after Year 5 after randomization according to procedures outlined in the Trial Flow Chart (see Section 6.3).

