7.1.2 Clinical Procedures/Assessments

7.1.2.1 Adverse Event Monitoring

All adverse events (AEs) will be recorded; the investigator or qualified designee will assess whether those events are drug-related (reasonable possibility, no reasonable possibility) and this assessment will be recorded in the database for all AEs. Adverse events will be graded and recorded throughout the study and during the follow-up period according to NCI CTCAE v4.0. Toxicities will be characterized in terms regarding seriousness, causality, toxicity grading, and action taken with regard to trial treatment. The collection period will begin during registration. All AEs must be followed until resolution or stabilization.

Hematological and biochemistry AEs will be assessed on the basis of regular blood counts. The nadir count will be computed at each study medication administration and graded according to the CTCAE v4.0 (see Section 7.2.4). Non-hematological acute side effects will be assessed and reported separately for each study medication administration and graded

according to the CTCAE v4.0. Post-treatment treatment-related late toxicity meeting serious criteria will be recorded as well up to 5 years.

Refer to Section 7.2 for detailed information regarding the assessment and recording of AEs.

7.1.2.2 12-Lead ECG

A standard 12-lead ECG will be performed using local standard procedures once at screening. Clinically significant abnormal findings should be recorded as medical history. Additional time points may be performed as clinically necessary.

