8.6.3 Statistical Methods for Safety Analyses

Safety and tolerability will be assessed by clinical review of all relevant parameters including AEs, laboratory tests, and vital signs.

AEs will be summarized overall and by the following time periods:

- Period of treatment with pembrolizumab/placebo in combination with CRT
- Period of maintenance with pembrolizumab/placebo
- Follow-up period with no treatment

The analysis of safety results will follow a tiered approach ([Table 26](#)). The tiers differ with respect to the analyses that will be performed. Adverse events (specific terms as well as system organ class terms) are either pre-specified as "Tier 1" endpoints or will be classified as belonging to "Tier 2" or "Tier 3" based on the number of events observed.

Tier 1 Events

Safety parameters or adverse events of interest that are identified a priori constitute “Tier 1” safety endpoints that will be subject to inferential testing for statistical significance. There are no Tier 1 events for this protocol as preliminary data from the MISP study [67] has demonstrated an acceptable and manageable safety/tolerability profile of pembrolizumab in combination with CRT for LA HNSCC.

Tier 2 Events

Tier 2 parameters will be assessed via point estimates with 95% CIs provided for differences in the proportion of subjects with events.

Membership in Tier 2 requires that at least 10% of subjects in any treatment group exhibit the specific AE; all other AEs will belong to Tier 3. The threshold of at least 10% of subjects was chosen for Tier 2 events because the population enrolled in this study is in critical condition and usually experiences various AEs of similar types regardless of treatment; events reported less frequently than 10% of subjects would obscure the assessment of the overall safety profile and add little to the interpretation of potentially meaningful treatment differences. In addition, 5% of subjects in any treatment group that exhibit a specific serious AE or a specific Grade 3-5 AE will be considered Tier 2 endpoints. Because many 95% CIs for Tier 2 events may be provided without adjustment for multiplicity, the confidence intervals should be regarded as a helpful descriptive measure to be used in review, not a formal method for assessing the statistical significance of the between-group differences in AEs and laboratory values that meet predefined limits of change.

Tier 3 Events

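### Active 5-year follow-up for treatment-related late SAEs appears to stop at the EFS event, and the no-treatment safety summaries make no allowance for unequal time at risk

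*Combined protocol and SAP*

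**What the plan says.** Section 3.2 makes safety a comparative secondary objective: "To evaluate and compare the safety and tolerability profile of pembrolizumab in combination with CRT" against placebo with CRT.

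The text on late serious toxicity falls into three groups.

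- **Active follow-up tied to a phase.** Section 7.2.4.1: "Subjects in post-treatment follow-up will be actively followed for treatment-related late serious adverse events for up to 5 years". Section 7.1.8.3.2 repeats the limit: "subjects in Post-Treatment Follow-Up will be followed for treatment-related late toxicities meeting serious criteria for up to 5 years". Section 5.10.1 gives subjects who stop treatment without an event "post-treatment follow-up for disease status until experiencing an event/disease progression, withdrawing consent or becoming lost to follow-up". Section 7.1.8.3.3.1 likewise ends imaging and clinical assessments at the event. After the event, under Section 7.1.8.3.4, "the subject enters the Survival Follow-Up Phase and should be contacted by telephone or have their medical records reviewed every 3 months". Those contacts cover survival, new anticancer therapy and, where no event has yet occurred, imaging or biopsy evidence. No toxicity item is listed.
- **Passive reporting with no time limit.** Section 7.2.4.1 also says that a related SAE that reaches the investigator later, "or at any time outside of the time period specified in the previous paragraph also must be reported immediately to the Sponsor".
- **Text that does not match the phase limit.** Section 7.1.2.1: "Post-treatment treatment-related late toxicity meeting serious criteria will be recorded as well up to 5 years", with no mention of phase. Section 6.3, footnote d, only permits this collection. Section 7.1.1.8 speaks of follow-up visits in the first five years for subjects who have had an event.

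On analysis, Section 8.6.3 summarizes AEs overall and by period, one of which is "Follow-up period with no treatment". Tier 2 gives differences in proportions with 95% CIs, and Tier 3 gives point estimates by arm. Section 8.12 describes exposure in treatment cycles only.

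**The concern.** Sections 5.2.2.3.16 and 5.8.3 expect late effects of radiotherapy such as persistent dysphagia and osteoradionecrosis. Section 5.2.1.2.1 notes that immune-related events may appear months after the last dose. These events fall largely in the period at issue.

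If active collection stops at the EFS event, the intensity of safety ascertainment depends on the primary efficacy endpoint. An arm with fewer or later EFS events spends longer under active questioning. A crude percentage then mixes the rate of late toxicity with the time spent looking for it. With equal true rates, the arm with better EFS would tend to show more late related SAEs. If pembrolizumab worsened EFS, some of its late toxicity would be less likely to be recorded. At stake is how late serious toxicity is read, not the EFS or OS tests.

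**Working it through.** **Inputs.** From Section 8.9: control EFS 70% at 12 and 40% at 36 months, piecewise exponential, HR 0.7; 10% dropout at 12 months; control OS 85%, 65% and 48% at 12, 36 and 96 months, HR 0.71; about 780 subjects, 1:1, 25 months of accrual. From Sections 5.2.2.1 and 7.2.4.1: about 12 months of treatment plus a 90-day all-cause SAE window, so late-only collection starts near month 15.

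**Assumptions, not in the documents.** The control EFS hazard continues past month 36 at its 12-36 month level. Five years means month 60 from randomization. A subject with an event before month 15 contributes no time. Dropout is ignored unless stated.

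**Step 1: reproduce the plan.** With drift √d·|ln 0.7|/2, the interim drift is √353 × 0.1783 = 3.351, and Φ(3.351 − 2.1517) = 0.8847 (plan 0.8841). The two-look calculation gives 0.9467 overall (plan 0.9463). The EFS curve with the stated accrual (last step 37.26 a month, to reach 780) and dropout gives 353.7 events at month 48 and 410.1 at month 60 (plan 353 and 410). The EFS model is therefore the plan's own.

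**Step 2: actively observed time, months 15 to 60.**
- Control: λ = ln(0.70/0.40)/24 = 0.02332 per month; S(15) = 0.6527; S(60) = 0.2286. Area = (0.6527 − 0.2286)/λ = 18.19 months.
- Pembrolizumab: hazard 0.7λ = 0.01632; S(15) = 0.7418; S(60) = 0.3559. Area = 23.65 months.
- Ratio 1.30, difference 5.46 months.

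**Step 3: follow-up to death or month 60.** The areas under the OS curves over the same window are 30.08 and 33.77 months, ratio 1.12. Active follow-up covers 18.19/30.08 = 60% and 23.65/33.77 = 70% of time alive. Stopping at the EFS event thus accounts for about 1.30/1.12 = 1.16; the rest comes from the assumed survival benefit.

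**Step 4: a different denominator.** For months 14 to 60 the areas are 18.85 and 24.39. Divided by the proportions event-free at month 14 (0.668 and 0.754), they give 28.2 and 32.3 months, ratio 1.15.

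**Step 5: sensitivity of the 1.30.**

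| Change | Ratio |
|---|---|
| 10% per year dropout | 1.29 |
| Data cut at month-60 final analysis (14.1 vs 17.7 months) | 1.25 |
| EFS HR 0.8 / 0.9 / 1.0 / 1.1 | 1.19 / 1.09 / 1.00 / 0.92 |
| Passive capture of 25% / 50% / 75% / 100% of post-event time | 1.24 / 1.19 / 1.15 / 1.12 |

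**Step 6: effect on crude percentages.** The documents give no late-SAE rate, so a range is assumed, equal in both arms, with no passive capture. For monthly rate h and EFS hazard λ, the recorded proportion is h·S(15)·[1 − exp(−45(h+λ))]/(h+λ). Differences are from unrounded values.

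| Assumed rate per 100 person-years | Control | Pembrolizumab | Difference (points) |
|---|---|---|---|
| 1 | 1.49% | 1.94% | 0.45 |
| 2 | 2.94% | 3.81% | 0.87 |
| 5 | 7.02% | 9.09% | 2.06 |
| 10 | 13.05% | 16.81% | 3.76 |

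With follow-up to death, the same rates would still give differences of 0.30, 0.59, 1.39 and 2.52 points. Extending collection alone would not remove the problem.

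**The case against.** The strongest counter-case has five parts.

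- **The end point is inferred.** No section defines post-treatment follow-up for late-SAE purposes. The Section 6.3 chart lists both continuous AE review and survival status, Section 7.1.2.1 sets no phase limit, and Section 5.10.1 keeps subjects who stop for progression under monitoring. This stands, so the point rests on the most direct reading.
- **Reporting continues.** A reader might infer that observation of late toxicity ends at the EFS event. The documents do not support that: related SAEs stay reportable at any time. What changes is active versus passive capture, and the completeness of passive capture is unknown.
- **The 1.30 is not all due to the EFS rule.** This stands (Steps 3 and 4). Section 8.6.3 states no denominator for the no-treatment period.
- **The affected tables are descriptive.** A between-arm CI for a specific serious AE needs at least 5% incidence in one arm. All late related SAEs together total only 1.5% to 17% under the assumed rates, so few single terms would qualify within that period. Section 8.6.3 itself says the intervals are not a formal method.
- **Asking about toxicity after the event has its own risk.** Section 7.1.7.2 allows unblinding after biopsy-proven progression, and many subjects will then be on new therapy. Attribution could differ by arm. This makes extended solicitation debatable. It applies to passive reports too, so they are not a clean substitute.

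These arguments limit the size and certainty of the concern. None of them answers the missing time-at-risk summary. The supplemental SAP is not among the documents and might contain one, though Section 8.6.3 does not defer to it.

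**Conclusion.** The point holds in a limited form. Read directly, active late-SAE follow-up ends at the EFS event, and the planned crude proportions for the no-treatment period do not account for it. At the design HR, actively observed time differs by a ratio of about 1.30 per randomized subject, with the lower figures given above under other denominators or capture assumptions. The percentages can therefore differ between arms without a true difference in late toxicity.

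Two stronger readings should be resisted. One is that pembrolizumab will look about 30% more toxic: that needs an EFS HR well below 1, a material late-SAE rate and poor passive capture. It disappears at HR 1 and reverses above it. The other is that the secondary safety comparison as a whole is biased: on-treatment safety and the 30/90-day reporting window are outside this point.

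The figures rest on the plan's EFS and OS assumptions, the extrapolation past month 36, and assumed late-SAE rates.

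**What to change.** **Analysis (Section 8.6.3).** For the no-treatment period, add one of the following beside the crude percentages:
- treatment-related late SAEs per 100 person-years of active toxicity follow-up, with numerator and denominator both limited to that time; or
- cumulative incidence with death as a competing event and censoring at the end of active follow-up.

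The rate assumes a roughly constant hazard within the period. Both methods describe toxicity while under active follow-up, so passive reports after the event should be listed separately.

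**Text.** Reconcile Section 6.3 footnote d with Sections 7.1.1.8, 7.1.2.1, 7.1.8.3.2, 7.1.8.3.4 and 7.2.4.1 on whether active late-SAE collection continues after an EFS event. If it does, show post-event reports separately by new anticancer therapy and by unblinding status.

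**Cost.** One extra table, and recording the end date of active toxicity follow-up. Amendment 08 states that the final efficacy analysis is complete, so any change to collection affects only the remaining follow-up. The adjusted summary can still be produced.
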